## **9.5 Screening logs**

Trial Torrent software will record the number of children with Read Codes suggesting a consultation for infected eczema each month, and these data will be used to assess for possible selection bias.

## **10 Withdrawal & loss to follow-up**

Parent/carer(s) will be informed that they have the right to withdraw consent for their child's participation in any aspect of CREAM Trial at any time. If a parent/carer indicates that they wish to withdraw their child from the trial they will be asked to give, though are not required to provide, a reason for withdrawal. The participants' care will not be affected by declining to participate or withdrawing from the trial.

If participants initially consent but subsequently withdraw from the trial, clear distinction must be made as to what aspect of the trial the participant is withdrawing from. These aspects could be:

- Withdrawing from trial treatment but happy to be followed up.
- Withdrawing from nurse follow-up (swabs and/or objective measures).
- Withdrawing from questionnaire/telephone follow-up.
- Withdrawing from all further follow-up.

A participant may be withdrawn from trial treatment for the following reasons:

- Withdrawal of consent for treatment by the parent/carer(s)
- Intolerance to trial medication
- Any alteration in the participant's condition, which, in the opinion of the patient's treating clinician, justifies the discontinuation of the treatment.

In all instances parent/carer(s) who consented will be asked to assist a member of the research team in completing a Withdrawal Form. Parent/carer(s) do not have to contribute to completing the Withdrawal Form. However, the PI in each site should ensure that a withdrawal form is completed as fully as possible and sent to the CREAM Trial Manager for every participant that withdraws.

## **11 Trial interventions**

The active medications being evaluated in this trial are well established and already widely used within their licensed indications. The active medications will not be used outside their licensed indication in the course of this trial. This is a study of their added value.

The trial has three treatment arms. Participants in all three treatment arms will receive a standard topical corticosteroid treatment for their eczema and comprehensive verbal and written eczema care instructions. All participants will also receive additional monitoring and support from a trained research nurse.

### **11.1 Treatments**

#### **11.1.1 Flucloxacillin suspension**

The flucloxacillin suspension used in this study is manufactured by Crescent Pharma Limited and has a Medicine and Healthcare products Regulatory Agency (MHRA) Marketing Authorisation (PL 20416/0077) (Appendix V). Flucloxacillin will be supplied as granules for reconstitution in 100ml to provide a concentration of 250mg/5mL to provide multiple doses as stated in Section 11.2. Flucloxacillin will be prescribed by the patient's clinician and prepared by the Site Pharmacy as described in Section 11.4.

#### **11.1.2 Erythromycin suspension**

The erythromycin suspension used in this study is manufactured by Amdipharm Plc and has a MHRA Marketing Authorisation (PL 20072/0042) (Appendix II). Erythromycin will be supplied as granules for reconstitution in 140ml to provide a concentration of 250mg/5mL to provide multiple doses as stated in Section 11.2. Erythromycin will be prescribed by the patient's clinician and prepared by the Site Pharmacy as described in Section 11.4.

#### **11.1.3 Fusidic acid cream**

The fusidic acid cream used in this study is supplied by St Mary's Pharmaceutical Unit, Cardiff (Appendix III). Fusidic acid will be supplied as 2% cream to provide multiple doses as stated in Section 11.2. Fusidic acid will be prescribed by the

patient's clinician and prepared by the Site Pharmacy as described in Section 11.4.

#### **11.1.4 Placebo suspensions**

The placebos for both flucloxacillin and erythromycin suspensions used in this study are manufactured by Tiofarma BV and supplied by Mawdsleys. Placebo to flucloxacillin will be supplied as granules for reconstitution in 100ml to provide multiple doses as stated in Section 11.2. Placebo to erythromycin will be supplied as granules for reconstitution in 140mL to provide multiple doses as stated in Section 11.2. Placebo suspensions will be prescribed by the patient's clinician and prepared by the Site Pharmacy as described in Section 11.4.

#### **11.1.5 Placebo cream**

The placebo cream used in this study is supplied by St Mary's Pharmaceutical Unit (SMPU). Placebo cream will be prescribed by the patient's clinician and prepared by the Site Pharmacy as described in Section 11.4.

## **11.2 Treatment arms**

### **11.2.1 Group 1: Oral Antibiotic and Topical Placebo**

- Oral antibiotic
  - Flucloxacillin 250mg per 5mL.
    - For children aged 3 months to 2 years - 2.5mL four times a day for 7 days.
    - For children aged over 2 years to under 8 years - 5mL four times a day for 7 days.
  - OR erythromycin 250mg per 5mL if penicillin allergy
    - For children aged 3 months to 2 years - 2.5mL four times a day for 7 days.
    - For children aged over 2 years to under 8 years - 5mL four times a day for 7 days.
- Topical placebo
  - Apply cream to affected area(s) three times a day for 7 days.

### **11.2.2 Group 2: Oral Placebo and Topical Antibiotic**

- Oral placebo
  - For children aged 3 months to 2 years - 2.5mL four times a day for 7 days.
  - For children aged over 2 years to under 8 years - 5mL four times a day for 7 days.
- Topical antibiotic - fusidic acid 2% cream

- Apply cream to affected area(s) three times a day for 7 days.

#### **11.2.3 Group 3: Oral Placebo and Topical Placebo**

- Oral placebo
  - For children aged 3 months to 2 years - 2.5mL four times a day for 7 days.
  - For children aged over 2 years to under 8 years - 5mL four times a day for 7 days.
- Topical placebo
  - Apply cream to affected area(s) three times a day for 7 days.

#### **11.2.4 Treatment for all patients in groups 1, 2 and 3:**

Participating clinicians will be asked to prescribe topical steroid (topical clobetasone butyrate 0.05% (Eumovate) cream or ointment (for eczema on trunk and/or limbs) and/or topical hydrocortisone 1% cream or ointment (for eczema on face)) for all the patients they refer to the CREAM trial. The treating clinician will need to choose between prescribing creams or ointments, and will be provided with guidance about best practice in relation to this decision.

### **11.3 Supply and packaging of Investigational Medicinal Product (IMP)**

SMPU, which is a pharmaceutical manufacturing facility and part of the Cardiff and Vale University Health Board, will acquisition and supply flucloxacillin and erythromycin in their original packaging. Mawdsleys will acquire, manufacture and stability test the bulk placebo for both flucloxacillin and erythromycin. These products will be manufactured in accordance with Good Manufacturing Practice (GMP) and the agreement between the Sponsor and Mawdsleys. SMPU will acquisition and stability test the placebo for fusidic acid in accordance with GMP and the agreement between the Sponsor and SMPU.

SMPU will reconcile all the IMPs into sealed and labelled 'Trial Packs' in accordance with their agreement with the Sponsor. Each batch of Trial Pack undergo release by a Qualified Person (QP) at SMPU to the Site Pharmacies in Wales, South West England and Scotland.

There will be six different Trial Packs (2 per treatment group) each labelled with a unique Trial Pack number:

Treatment Group	Treatment Pack Group Letter	IMP in Trial Pack
1	A	Oral active (Flucloxacillin) powder in original packaging for reconstitution to 100ml oral solution 250mg/5ml, and a labelled empty bottle; topical placebo cream (30g).
	B	Oral active (Erythromycin) powder in original packaging for reconstitution to 140mL oral solution 250mg/5ml, and a labelled empty bottle; 2 x 30g topical placebo cream.
2	C	Oral placebo (to Flucloxacillin) powder in a labelled bottle dispensing the reconstituted 100ml oral solution; 30g topical Fusidic Acid cream (2%).
	D	Oral placebo (to Erythromycin) powder in a labelled bottle dispensing the reconstituted 140ml oral solution; 2 x 30g topical Fusidic Acid cream (2%).
3	E	Oral placebo (to Flucloxacillin) powder in a labelled bottle dispensing the reconstituted 100ml oral solution; 30g topical placebo cream.
	F	Oral placebo (to Erythromycin) powder in a labelled bottle dispensing the reconstituted 140ml oral solution; 2 x 30g topical placebo cream.

An example of other items each pack will contain:

- i. Empty bottle matched to the placebo bottles.
- ii. Bottle adaptor for syringe insertion.
- iii. Oral delivery syringe.
- iv. Labels to mark syringe for dosage variations.
- v. Patient information leaflet (PIL) with instructions for use.

The primary packaging of all IMPs will state 'for clinical trial use only'. Also included on the label will be the name of the Co-chief investigators, the expiry date of the product, the batch number (relating to assembly) and a unique identifier for that tube/bottle. As the active antibiotics are being compared to placebo, to maintain blinding the IMPs will not be labelled for their content on any label on the primary or secondary packaging.

Trial materials will be stored under the conditions specified by the manufacturer (or in the Summary Product Characteristics (SmPCs)) by SMPU. Trial Packs will be distributed from SMPU to the site pharmacies as required, following a request from Site Pharmacy to the CREAM Trial Manager. Upon receipt by the Site Pharmacy, all clinical materials will be stored in a designated temperature monitored area within the pharmacy.

## **11.4 Prescribing, distribution and use of the IMP**

The process of prescribing, dispensing and return of IMP is described in detail in the Pharmacy Manual.

The patient will visit their General Practice for an appointment. If their clinician (GP/Nurse Prescriber) suspect infected eczema, the clinician will complete the CREAM Prescription Form and refer the patient to the research nurse. (Erythromycin (or its placebo) will only be prescribed if the patient is known to be allergic to penicillin). The prescription will be faxed to the local trial pharmacy for preparation.

If the Site Pharmacy is dispensing flucloxacillin or erythromycin, the pharmacist will prepare the antibiotic suspension by reconstituting in the original primary packaging and decanting into a fresh bottle matched to the placebo, which will be provided in the Trial Pack.

If the clinician has prescribed the larger dosage of flucloxacillin (5mL four times a day) of oral antibiotic (or its placebo) then two identical Trial Packs will be prepared to ensure sufficient volume for a one week course.

The research nurse will collect the Trial Pack(s) from the pharmacy and deliver to the participant at the baseline visit, within 72 hours of the IMP being prescribed and on the same day that the IMP is reconstituted. The IMP will be issued to the participant at the baseline visit with instructions for use and a Patient Information Leaflet (PIL) about the potential IMP (for both active and its placebo medicine) (Appendix VI).

## **11.5 Interaction with other drugs**

There is a negligible chance of interaction with other drugs. The active antibiotics are commonly used and have known safety profiles. As a precaution, listed below are medications that are known to interact with the study medication. However, it is unlikely any patient will be referred to the CREAM study if their condition requires use of the medication listed below. Any patient taking these medications will most likely not fulfil the CREAM inclusion and exclusion criteria, and therefore not be included in the study.

All participants should avoid:

- Ritonavir
- Simvastatin

Participants allergic to penicillin (who may receive erythromycin) should avoid the medicines listed below due to their interactions with erythromycin:

• Amiodarone	• Disopyramide	• Reboxetine
• Amiodarone	• Dronedarone	• Rifabutin
• Amisulpiride	• Droperidol	• Saquinavir
• Arsenic Trioxide	• Ergotamine and Methysergide	• Simvastatin
• Artemether with Lumefantrine	• Eletriptan	• Sirolimus
• Atomoxetine	• Everolimus	• Sulpiride
• Carbamazepine	• Ivabradine	• Tacrolimus
• Ciclosporin	• Midazolam	• Theophyline
• Clopidogrel	• Mizolastine	• Verapamil
• Clozapine	• Moxifloxacin	• Vinblastine
• Colchicine	• Pentamidine Isetionate	• Zuclopentixol
• Coumarins	• Pimozide	

## 12 Pharmacovigilance

### 12.1 Definitions

The following definitions are in accordance with both the Medicines for Human Use (Clinical Trials) Regulations 2004 (SI2004/1031) and the subsequent amendment regulations (SI2006/1938) and ICH-GCP:

#### 12.1.1 Adverse Event (AE)

Any untoward medical occurrence in a clinical trial participant to whom an IMP has been administered and which does not necessarily have a causal relationship with this treatment. An AE can therefore be any unfavourable and unintended sign (including abnormal laboratory finding), symptom, or disease.

#### 12.1.2 Adverse Reaction (AR)

Any noxious and unintended response in a clinical trial participant to whom an IMP has been administered, which is related to any dose administered. A "response" to a medicinal product means that a causal relationship between a

medicinal product and an adverse event is at least a reasonable possibility, i.e. the relationship cannot be ruled out.

### **12.1.3 Serious Adverse Event (SAE)**

Any adverse event that:

- Results in death
- Is life-threatening\*
- Required hospitalisation or prolongation of existing hospitalisation\*\*
- Results in persistent or significant disability or incapacity
- Consists of a congenital anomaly or birth defect
- Other medically important condition \*\*\*

\* Note: The term "life-threatening" in the definition of serious refers to an event in which the participant was at risk of death at the time of the event; it does not refer to an event which hypothetically might have caused death if it were more severe.

\*\* Note: Hospitalisation is defined as an inpatient admission, regardless of the length of stay, even if the hospitalisation is a precautionary measure, for continued observation. Pre-planned hospitalisation e.g. for pre-existing conditions which have not worsened or elective procedures does not constitute an adverse event.

\*\*\* Note: other events that may not result in death are not life-threatening, or do not require hospitalisation may be considered as a serious adverse event when, based upon appropriate medical judgement, the event may jeopardise the participant and may require medical or surgical intervention to prevent one of the outcomes listed above.

### **12.1.4 Serious Adverse Reactions (SARs)**

Any Serious Adverse Event occurring in a clinical trial participant for which there is a reasonable possibility that it is related to the IMP at any dose administered.

### **12.1.5 Suspected Unexpected Serious Adverse Reactions (SUSAR)**

These are **SARs** which are classified as 'unexpected', i.e. an adverse reaction, the nature and severity of which is not consistent with the information about the medicinal product outlined in the Investigator Brochure (IB) and SmPCs.

Example expected adverse reactions with trial treatments are listed below (and provided in detail in each medicine's SmPC):

- *Oral erythromycin*

Disorder	Examples
Blood and lymphatic system	Eosinophilia
Cardiac	QTc interval prolongation, torsades de pointes, palpitations, and cardiac rhythm disorders including ventricular tachyarrhythmias
Ear and labyrinth	Deafness, tinnitus (There have been isolated reports of reversible hearing loss occurring chiefly in patients with renal insufficiency or taking high doses.)
Gastrointestinal	Upper abdominal discomfort, nausea, vomiting, diarrhoea, pancreatitis, anorexia, infantile hypertrophic pyloric stenosis, Pseudomembranous colitis
General disorders and administration site conditions	Chest pain, fever, malaise
Hepatobiliary disorders	Cholestatic hepatitis, jaundice, hepatic dysfunction, hepatomegaly, hepatic failure, hepatocellular hepatitis
Immune system disorders	Allergic reactions ranging from urticaria and mild skin eruptions to anaphylaxis
Investigations	Increased liver enzyme values
Nervous system disorders	Isolated reports of transient central nervous system side effects including confusion, seizures and vertigo. (A cause and effect relationship has not been established.)
Psychiatric disorders	Hallucinations
Renal and urinary disorders	Interstitial nephritis
Skin and subcutaneous tissue disorders	Skin eruptions, pruritus, urticaria, exanthema, angioedema, Stevens-Johnson syndrome, toxic epidermal necrolysis, erythema multiforme
Vascular disorders	Hypotension

- *Oral flucloxacillin*

Disorder	Examples
Blood and lymphatic system	Neutropenia (including agranulocytosis), thrombocytopenia, haemolytic anaemia.
Immune system	Anaphylactic shock (exceptional with oral administration), angioneurotic oedema
Gastrointestinal	Minor gastrointestinal disturbances, Pseudomembranous colitis
Hepato-biliary	Hepatitis and cholestatic jaundice
Skin and subcutaneous tissue	Rash, urticaria and purpura Erythema multiforme, Stevens-Johnson syndrome and toxic epidermal necrolysis
Musculoskeletal and connective tissue	Arthralgia, myalgia
Renal and urinary	Interstitial nephritis
General disorders and administration site conditions	Fever

- *Topical fusidic acid*

Disorder	Examples
Immune system	Hypersensitivity

Eye	Conjunctivitis
Skin and subcutaneous tissue	Pruritus, rash including erythematous, maculo-papular and pustular reactions, contact dermatitis, irritation at site of application (including pain, stinging, burning and erythema).

## 12.2 Causality

Most adverse events and drug reactions that occur in this study, whether they are serious or not, will be expected treatment-related toxicities due to the drugs used in this study. The assignment of the causality should be made by the investigator responsible for the care of the participant using the definitions in the table below.

Relationship	Description
Unrelated	There is no evidence of any causal relationship
Unlikely	There is little evidence to suggest there is a causal relationship (e.g. the event did not occur within a reasonable time after administration of the trial medication). There is another reasonable explanation for the event (e.g. the participant's clinical condition, other concomitant treatment).
Possible	There is some evidence to suggest a causal relationship (e.g. because the event occurs within one week after administration of the trial medication). However, the influence of other factors may have contributed to the event (e.g. the participant's clinical condition, other concomitant treatments).
Probable	There is evidence to suggest a causal relationship and the influence of other factors is unlikely.
Definitely	There is clear evidence to suggest a causal relationship and other possible contributing factors can be ruled out.
Not assessable	There is insufficient or incomplete evidence to make a clinical judgement of the causal relationship.

If any doubt about the causality exists, the local investigator should inform the study coordination centre who will notify the Chief Investigator(s). The pharmaceutical companies and/or other clinicians may be asked to advice in some cases.

The assignment of the causality should be made by the Investigator responsible for the care of the participant.

The Chief Investigator (or Clinical Reviewer Delegate) will also be responsible for making an assessment of causality.

In the case of discrepant views on causality between the investigator and others, all parties will discuss the case. In the event that no agreement is made, the local site investigator/PI's views will prevail and the MHRA will be informed of this view.

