#### **12.4.2 Serious AR/AEs**

Fatal or life-threatening SAEs and SUSARs should be reported to the Trial Manager within 24 hours of the local site becoming aware of the event. The SAE form asks for the nature of event, date of onset, severity, corrective therapies given, outcomes and causality (i.e. unrelated, unlikely, possible, probably, definitely). The responsible investigator should sign the causality of the event. An SAE form should be completed and faxed to the study coordination centre for all SAEs within 24 hours. Additional information should be sent within 5 days if the

reaction has not resolved at the time of reporting. SAE reporting and processing procedures will be included in the training of all sites and research site staff.

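### The causality tie-break in section 12.2 lets a local 'not related' override a Chief Investigator's 'possible', so a serious unexpected event need not enter the SUSAR route

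*Protocol*

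**What the plan says.** Section 12.2 makes the investigator responsible for the participant's care the assessor of causality, on a six-category scale from *unrelated* to *definitely* plus *not assessable*. It then adds a second assessor: "The Chief Investigator (or Clinical Reviewer Delegate) will also be responsible for making an assessment of causality". If views differ there is a first step, "In the case of discrepant views on causality between the investigator and others, all parties will discuss the case", and then a tie-break: "In the event that no agreement is made, the local site investigator/PI's views will prevail and the MHRA will be informed of this view".

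The definitions that this assessment feeds are in section 12.1:

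- Adverse reaction (12.1.2): the causal relationship is "at least a reasonable possibility, i.e. the relationship cannot be ruled out".
- Serious adverse reaction (12.1.4): a serious event "for which there is a reasonable possibility that it is related to the IMP at any dose administered".
- SUSAR (12.1.5): serious adverse reactions "which are classified as 'unexpected', i.e. an adverse reaction, the nature and severity of which is not consistent with the information" in the reference documents.

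Section 12.3 reserves expectedness to the Chief Investigator or delegate and applies that step to adverse reactions. Section 12.4.3 applies the SUSAR procedure to events that are serious, unexpected and related, and its 7- and 15-day limits cover SUSARs only. Section 12.4.2 sends all SAEs to the coordination centre within 24 hours. It lists the content of the SAE form as including "causality (i.e. unrelated, unlikely, possible, probably, definitely", which is five categories.

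**The concern.** The threshold in the definitions is low by design: a relationship counts unless it can be excluded. The tie-break can work against that. When the designated second assessor has discussed the case and still holds that a relationship is possible, it is hard to maintain that it has been excluded. Yet section 12.2 settles the matter as not related if that is the local view.

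What is at stake is expedited reporting of a serious, unexpected event in a placebo-controlled trial of children from 3 months of age. The Chief Investigator alone judges expectedness, but that judgement is called for only once an event counts as an adverse reaction. A local *unrelated* can therefore stop the event before the central judgement is reached.

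A smaller mismatch lies beside it. *Not assessable* is a permitted rating in section 12.2 but is absent from the list in section 12.4.2, and nothing says how such a rating is treated for reporting.

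**Working it through.** The plan states no figure on this point and no arithmetic applies. The check is to follow each pair of opinions through the rules.

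**Assumption.** The protocol does not say where its causality scale divides into related and not related. I take *possible* or higher as related and *unrelated* or *unlikely* as not related.

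**Rules applied, in order.** (a) The tie-break in 12.2. (b) Reaction or not, under 12.1.2 and 12.1.4. (c) Expectedness under 12.3, for reactions. (d) The SUSAR route and the 7/15-day limits in 12.4.3, for events that are serious, related and unexpected.

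| Case | Investigator | Chief Investigator | Outcome after tie-break | SUSAR report if unexpected? |
|---|---|---|---|---|
| 1 | related | related | SAR | yes |
| 2 | related | not related | investigator prevails: SAR | yes |
| 3 | not related | related | investigator prevails: not a SAR | not required |
| 4 | not related | not related | not a SAR | no |

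**Case 2.** The rule is protective: the centre cannot lower a local *related* rating.

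**Case 3.** The Chief Investigator's higher rating is overridden. Because the event is not classed as a reaction, step (c) is not called for and step (d) does not apply. Set beside this, section 12.1.2 asks whether the "medicinal product and an adverse event is at least a reasonable possibility, i.e. the relationship cannot be ruled out", and section 12.1.4 asks whether there is a reasonable possibility of relation. One of the two named assessors has answered yes to both.

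**Does other text close case 3?**

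- Section 12.4.2 brings every SAE to the coordination centre within 24 hours, so the event is known centrally. It does not change the classification.
- Section 12.2 has the MHRA informed of the prevailing view. It gives no timeline or format, does not say that the differing opinion goes with it, and does not mention the ethics committee.
- Section 19.1 has the Trial Management Group review and advise on SAE reporting, and section 20.2 has the IDMC review data periodically. Neither is given power to override section 12.2.

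**Category lists.** Section 12.2 has six: *unrelated*, *unlikely*, *possible*, *probable*, *definitely*, *not assessable*. Section 12.4.2 has the first five. A rating of insufficient evidence does not exclude a relationship, so its handling matters under the section 12.1.2 test.

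**The case against.** The strongest reply is that the definitions name no assessor, while section 12.2 twice assigns causality to the investigator. On that reading no two sentences contradict each other: the investigator's judgement decides whether a relationship can be excluded. This stands to the extent that the conflict is one of operation, not of wording. It does not explain why a second assessor is appointed whose positive finding has no effect on classification.

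Several safeguards also stand. Doubt about causality is to be raised with the coordination centre and the Chief Investigator, other clinicians or the companies may be asked to advise, and discussion comes before the tie-break. The prevailing voice may be the Principal Investigator's, who under sections 6 and 7.1 leads a region, so it need not be that of a clinician who has seen one case. The drugs are established and section 12.1.5 lists broad expected reactions, so few events would be unexpected. These points make case 3 rarer; they do not remove it. The reporting flowchart (Figure 2) and the SAE form are not visible here, and either might treat disputed cases or *not assessable* differently.

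Stronger readings are tempting but not supported:

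- A reader might infer that events are downgraded. No rating is lowered: the investigator's rating stands and the higher one is not adopted.
- A reader might infer that such an event can never be reported as a SUSAR, or that the MHRA hears the local view alone. The text requires that the local view be passed on. It neither forbids passing on the other view nor bars a report; it simply does not require one.
- A reader might try to express the loss as a share of all SAEs. That would need an SAE rate, which the documents do not give, and would still say nothing about how often disagreement goes unresolved.

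**Conclusion.** The point holds in a limited form. In one of four combinations of opinion, a serious event that the Chief Investigator considers possibly drug-related need not be handled as a SAR or, if unexpected, reported within 7 or 15 days. That outcome fits poorly with the protocol's own test for a reaction, and no visible provision overrides it. It follows from a rule the protocol states, so it is not a detail left to another document.

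The conclusion assumes that *possible* or higher means related, that discussion has failed, and that the unseen flowchart does not say otherwise. The frequency is unknown and probably low. Sample size, alpha, power and the efficacy analysis are unaffected. The amendment should be made, because it is cheap and concerns safety reporting in young children. The mismatch in category lists is real but minor.

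**What to change.** Replace the tie-break sentence in section 12.2 with a rule to this effect: *An SAE that either the investigator or the Chief Investigator (or delegate) considers at least possibly related is handled as a SAR and assessed for expectedness. A rating of related given by the investigator is not lowered. If the two opinions differ, both are stated in any report to the MHRA and the REC.* This keeps the protection in case 2 and closes case 3.

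State which categories count as related. Reconcile the six categories in section 12.2 with the five in section 12.4.2, and say how *not assessable* is handled for reporting. Check Figure 2 and the SAE form against the amended text.

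The cost is one amended paragraph, an aligned category list and an occasional extra expedited report.
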